Genotyping - Confirmation of patient's HoFH status can be made by either genetic or clinical criteria. If HoFH diagnosis cannot be confirmed by the clinical criteria listed or from previous genotyping results, patients may enter the run-in period to determine their mutation status.

Screening Period:

Patients who are required to enter a 2-week screening period:

- Evinacumab treatment-naïve patients.
- Patients from a previous evinacumab study who do not enter this study within 7 days of completing the end of study (EOS) visit of the previous study.

Open-Label Treatment Period:

Patients who completed the EOS visit in the previous evinacumab study within 7 days of the baseline/day 1 visit for this open label study do not have to undergo the screening visit and may enroll directly into this study if they fulfill all of the inclusion criteria and none of the exclusion criteria.

The EOS visit from the previous study can serve as the baseline/day 1 visit for this open-label study and overlapping assessments do not need to be repeated in this study. Baseline assessments and procedures that do not overlap with assessments at the EOS visit of the previous study should be performed after all EOS assessments and procedures have been completed in the previous evinacumab study.

Starting on day 1 (baseline), patients will receive evinacumab 15 mg/kg IV administered Q4W (± 7 days) at the study site. Patients will remain in the clinic for monitoring for 60 minutes after the end of each IV infusion. For patients unable to go to the site, evinacumab may be administered at an alternative location, which could include the patient's home by a trained nurse or other health professional, as allowed by local laws.

All patients who were supplied with alirocumab 150 mg subcutaneous (SC) by the sponsor in a previous study may continue to be provided with alirocumab 150 mg SC every 2 weeks (Q2W) in this study. Those entering this study, after completing a study evaluating the safety and efficacy of alirocumab in patients with HoFH, but did not participate in a prior evinacumab study, may or may not remain on alirocumab as part of their background LMT.

Based on the patient's preference and the judgment of the investigator and the patient's health care provider, each patient may:

- continue treatment with alirocumab supplied by the sponsor as part of their background LMT
- discontinue alirocumab prior to enrolling

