9.4.3. Other Events that Require Accelerated Reporting to Sponsor

The following events also require reporting to the sponsor (or designee) within 24 hours of learning of the event:

Symptomatic Overdose of Study Drug: Accidental or intentional overdose of at least 2 times the intended dose of study drug within the intended therapeutic window, if associated with an AE,

Pregnancy: Although pregnancy is not considered an AE, it is the responsibility of the investigator to report to the sponsor (or designee), within 24 hours of identification, any pregnancy occurring in a female patient or female partner of a male patient, during the study or within 24 weeks of the last dose of study drug. Any complication of pregnancy affecting a female study patient or female partner of a male study patient, and/or fetus and/or newborn that meets the SAE criteria must be reported as an SAE. Outcome for all pregnancies should be reported to the sponsor.

Adverse Events of Special Interest: All AESI, serious and nonserious, must be reported within 24 hours of identification using the same reporting process as for SAE reporting, per Section 9.4.2.

Adverse events of special interest for evinacumab include the following:

- Anaphylactic reactions
- Moderate or severe infusion reactions

- Increase in ALT or AST: ≥ 3 x ULN (if baseline <ULN), or ≥ 2 times the baseline value (if baseline \geq ULN)
- Allergic events and/or local injection site reactions that require medical treatment or that require consultation with another physician for further evaluation
- Pregnancy
- Symptomatic overdose with investigational medicinal product
- Neurocognitive events
- New onset of diabetes*
- Pancreatitis

Adverse events of special interest for alirocumab include the following:

- Increase in ALT: ALT ≥ 3 x ULN (if baseline ALT <ULN), or ALT ≥ 2 times the baseline value (if baseline ALT \geq ULN)
- Allergic events and/or local injection site reactions that require consultation with another physician for further evaluation
- Pregnancy
- Symptomatic overdose with investigational medicinal product
- Neurologic events that require additional examinations/procedures and/or referral to a specialist
- Neurocognitive events
- Cataracts
- New onset of diabetes*

*New onset of diabetes is defined as any of the following:

- Type 1 or type 2 diabetes TEAE (grouping of MedDRA terms will be specified in the statistical analysis plan [SAP])

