4.8.1.2. Adverse Events of Special Interest

Adverse events of special interest (AESI) are AEs (serious or non-serious) required to be monitored, documented, and managed in a pre-specified manner. AESIs will be recorded on the adverse event e-CRF using dedicated tick boxes, and/or identified using standard MedDRA queries (SMQ), company MedDRA queries (CMQ), MedDRA terms, and/or applicable laboratory assessments. Appendix 10.3 contains the definitions used to identify AESIs:

The AESIs include:

- Anaphylactic reactions (e-CRF)
- General allergic events (SMQ)
- Infusion reactions (e-CRF)
- Hepatic Disorder (SMQ, lab data)
- Pregnancy (e-CRF)
- Symptomatic overdose with investigational medicinal product (e-CRF)
- Neurocognitive events (CMQ)
- Neurologic events (e-CRF)
- New onset of diabetes (NOD) (lab data, MedDRA HLT, concomitant medications) for patients without diabetes mellitus at baseline
- Diabetic complication (CMQ, concomitant medications) for patients with diabetes mellitus at baseline
- Pancreatitis (e-CRF)
- Cataracts (MedDRA HLT)
- Immune complex diseases (SMQ)
- Muscle events/CK elevation (MedDRA SOC, SMQ, lab data)

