5.8.1. Adverse Events

In general, the primary focus of AE reporting will be on TEAEs summarized in TEAE period. Post-treatment AEs will be summarized separately.

If an AE onset date (occurrence, worsening, or becoming serious) is incomplete, an imputation algorithm will be used to classify the AE as pre-treatment, treatment-emergent, or post-treatment. The algorithm for imputing date of onset will be conservative and will classify an AE as treatment-emergent unless there is definitive information to determine pre-treatment or post-treatment status. Details on classification of AEs with missing or partial onset dates are provided in Section 6.3.

Adverse event incidence tables will present the number (n) and percentage (%) of patients experiencing an AE by SOC and PT. In addition, incidence tables by SOC, HLG, HLT, and PT will be provided for all TEAEs, serious TEAEs, and TEAEs leading to permanent treatment discontinuation. Multiple occurrences of the same event in the same patient will be counted only once in the tables within a treatment phase (TEAE or post-treatment AE). For tables presenting by severity of events, the worst severity will be chosen for patients with multiple instances of the same event. The denominator for computation of percentages is the safety analysis set within each patient group, and again for the subpopulation of adolescent patients.

AE incidence tables will present data by SOC sorted alphabetically and PT sorted by decreasing frequency of the overall patient, and summarize the number (n) and percentage (%) of patients experiencing an AE.

The event rate per patient-year (the number of patients with an event divided by total patient-years) will be provided in the table for all TEAEs by SOC and PT. For a patient with an event, patient-year is censored at time of first event. For a patient without an event, patient-year corresponds to the length of the TEAE period.

Analysis of all treatment-emergent adverse events

The following TEAE summaries will be generated:

- Overview of TEAEs, summarizing number (%) of patients with any
 - TEAE;
 - Serious TEAE;
 - TEAE leading to death;
 - TEAE leading to permanent treatment discontinuation.
- All TEAEs by primary SOC, HLG, HLT, and PT
- All TEAEs by primary SOC and PT
- Number (%) of patients experiencing common TEAE(s) presented by primary SOC and PT (PT incidence $\geq 5\%$ in any patient group)
- All TEAEs relationship (related/not related) to evinacumab

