5.8.2. Analysis of Adverse Events of Special Interest

- Treatment-emergent adverse events of special interest (AESI), as listed in Section 4.8.1.2, will be presented by SOC and PT as applicable. AESI are defined by SMQ, CMQ, and/or dedicated e-CRF as described in Appendix 10.3 .

The following variables will also be tabulated for infusion reactions TEAEs:

- Intensity of the event (mild, moderate, severe or very severe);
- Number of events divided by the number of study treatment administrations received in treatment period;
- Time from first study treatment to first infusion reaction;

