10.3. List of AESIs with Data Sources and Definitions of SMQ/CMQ

Table 2: Summary of AESIs and the Methods of Data Collections and Derivations

AESI	Using an e-CRF specific tick box on AE page	Using Standard MedDRA Query (SMQ)/company MedDRA Query (CMQ) or lab data
Anaphylactic reactions	Yes	No
General allergic events	No	SMQ “hypersensitivity” (broad and narrow) excluding the following preferred terms linked to local injection site reactions (“infusion site dermatitis”, “infusion site hypersensitivity”, “infusion site rash”, “infusion site urticaria”, “injection site dermatitis”, “injection site hypersensitivity”, “injection site rash”, “injection site urticaria”, “injection site vasculitis”) plus “idiopathic angioedema”
Infusion reactions	Yes	No
Hepatic Disorders	No	
 • SMQ Drug-related hepatic disorder • Potentially clinically significant value (PCSV) in Appendix 10.4 • Hy’s law eDISH plot
Pregnancy	Yes	No
Symptomatic overdose with investigational medicinal product	Yes	No
Neurocognitive events	Yes	
 • CMQ for neurocognitive events as defined based on Regulatory Agency request for another lipid lowering program (See Table 3 in Appendix 10.3 for the list of terms)
Neurologic events	Yes	No

AESI	Using an e-CRF specific tick box on AE page	Using Standard MedDRA Query (SMQ)/company MedDRA Query (CMQ) or lab data

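### Neurologic events are a protocol AESI only for alirocumab, yet the SAP counts them by tick box alone across the whole safety set, so the AESI line may miss events in patients not on alirocumab

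*SAP*

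**What the plan says.** Protocol 9.4.3 has two AESI lists. The first opens "Adverse events of special interest for evinacumab include the following" and has nine items. Neurocognitive events are among them; neurologic events are not. The second opens "Adverse events of special interest for alirocumab include the following" and contains "Neurologic events that require additional examinations/procedures and/or referral to a specialist". That is the only place in 9.4.3 where neurologic events appear.

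The SAP has one combined list for the study. Section 4.8.1.2 enters the item as "Neurologic events (e-CRF", without the work-up or referral condition and without reference to alirocumab. The row in Appendix 10.3 Table 2 is "Neurologic events Yes No": yes for the tick box, no for an SMQ, CMQ or laboratory search.

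For the analysis, SAP 5.8.2 states that "AESI are defined by SMQ, CMQ, and/or dedicated e-CRF as described in Appendix 10.3". SAP 5.8 presents safety summaries in the safety analysis set by patient group, and SAP 5.8.1 says "The denominator for computation of percentages is the safety analysis set within each patient group". No subset of alirocumab users is defined. SAP 1.2.3 declares no modification from the protocol's statistical section.

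Alirocumab is optional background therapy. Under Protocol 5.1, patients coming from an alirocumab study "may or may not remain on alirocumab as part of their background LMT", and Protocol 3.2.3 allows evolocumab instead.

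**The concern.** The population covered by the AESI line and the population for which the protocol asks that these events be flagged are not the same. For a patient not on alirocumab, 9.4.3 gives the investigator no instruction to treat a neurologic event as an AESI. The SAP still puts that patient in the denominator and finds the event only if someone ticked the box. SAP 6.3 has no rule for an unticked box, so in this line it would count as no event.

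The category is one the sponsor reports on. Protocol section 1 names neurologic events among the topics that raised no safety concern in the parent study R1500-CL-1629. A similar statement from this study, drawn from the AESI line, could rest on uneven ascertainment. A low or zero count might then reflect who was asked to tick the box rather than how often the events occurred.

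**Working it through.** Neither document states an expected rate, a precision or a sample-size figure for this AESI, so there is no plan figure to reproduce. The check has two parts.

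**1. Comparing the lists.** SAP Table 2 has six rows that rely on the tick box alone: anaphylactic reactions, infusion reactions, pregnancy, symptomatic overdose, neurologic events and pancreatitis. Five of these are on the protocol's evinacumab list, so every investigator is told to report them (for infusion reactions, only moderate or severe ones). Neurologic events are the sixth, and the only one missing from that list. Two neighbouring items show the contrast. Cataracts are also on the alirocumab list only, but the SAP finds them by MedDRA HLT in everyone. Neurocognitive events have a tick box and also a CMQ.

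**2. Possible size.** Inputs:
- N = 120, the approximate planned enrolment (SAP 2.2).
- f, the share of patients on alirocumab: not in the documents; assumed 0.10 to 0.50.
- g, the share of events still ticked in patients not on alirocumab: not in the documents; assumed 0 to 1.
- p, the true incidence: not in the documents; assumed 5% (2% and 10% as variants), the same in users and non-users.

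All events in alirocumab users are taken as ticked. Then:
- reported rate = p × [f + (1 − f)g]
- reported/true ratio = f + (1 − f)g
- chance that no patient is flagged = (1 − reported rate)^120

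Example: f = 0.25 and g = 0.5 give 0.25 + 0.75 × 0.5 = 0.625. At p = 5% the reported rate is 3.125%, or 3.75 patients of 120 instead of 6.0.

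Results at p = 5%:

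| f | g | ratio | expected patients flagged | chance of none flagged |
|---|---|---|---|---|
| 0.10 | 0 | 0.10 | 0.6 | 0.548 |
| 0.10 | 0.5 | 0.55 | 3.3 | 0.035 |
| 0.25 | 0 | 0.25 | 1.5 | 0.221 |
| 0.25 | 0.5 | 0.625 | 3.75 | 0.022 |
| 0.50 | 0 | 0.50 | 3.0 | 0.048 |
| 0.50 | 0.5 | 0.75 | 4.5 | 0.010 |
| any | 1 | 1.00 | 6.0 | 0.002 |

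The ratio does not depend on p, but the chance of a zero count does. With f = 0.25 and g = 0, that chance is 0.548 at p = 2% (0.089 if all events are ticked) and 0.048 at p = 10% (below 0.001 if all are ticked).

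**The case against.** A reader might infer that the reported evinacumab rate must be too low by construction, equal to the true rate times the alirocumab share. The documents do not support that. It needs g = 0, meaning that sites leave the box blank for every patient not on alirocumab, and no section says so. Protocol 9.4.3 governs accelerated reporting to the sponsor, not completion of the AE page. SAP 4.8.1.2 describes the tick boxes without tying any of them to alirocumab. The e-CRF completion instructions are not among the documents. If the box is completed for everyone, the ratio is 1.00 and nothing is lost. This objection stands: it reduces a certainty to a possibility.

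A reader might also infer that the primary safety endpoint is compromised. It is not. All AEs are recorded in every patient (Protocol 9.4.1), and all TEAEs are tabulated by SOC and PT (SAP 5.8.1), so an unticked neurologic event still appears there. Only the AESI line is exposed.

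Two further arguments carry less weight. First, the SAP's AESI list is in any case wider than 9.4.3: diabetic complications, immune complex diseases and muscle events are on neither protocol list. But Table 2 finds those three from coded terms, laboratory data or medication records, so they do not depend on an investigator's flag. Second, the parent-study statement on neurologic events is not limited to alirocumab users, which suggests that the category is followed more generally. It does not say how those events were identified.

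The SAP was approved on 31 October 2019 and appends the schedules of Amendments 5A and 5B, so it predates the current protocol. The amendment log records the addition of infusion reactions to the AESIs but no change to the neurologic item, so it does not explain the mismatch.

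**Conclusion.** The mismatch is established from the text. The protocol makes neurologic events an AESI for alirocumab only, and under a condition; the SAP drops the condition, applies the item to the whole safety set and finds it by tick box alone. What follows is a possibility: the AESI line may under-ascertain these events in patients not on alirocumab. The loss ranges from none (g = 1) to a fraction 1 − f of the true incidence (g = 0), and neither f nor g is given. The low-g rows of the table are worst cases on assumed inputs, not estimates. The general TEAE tables stand as they are. This is a cheap improvement to one AESI row, not a flaw in the primary analysis.

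**What to change.** In SAP Appendix 10.3 Table 2, add a pre-specified MedDRA grouping for neurologic events and apply it to all patients in the safety analysis set, following the approach already used for neurocognitive events and cataracts. Report the tick-box AESI as a separate row, labelled with the protocol's work-up or referral condition, and restrict both its numerator and its denominator to patients receiving alirocumab. Restricting the denominator alone would be wrong if some boxes were ticked in other patients. The SAP should also state how receipt of alirocumab is determined from the medication records.

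The cost is SAP wording and one extra table row from AEs that are already coded. The coded-term row has limits: it is broader than the protocol's AESI because coded terms cannot show whether an event led to work-up or referral, it partly overlaps the SOC and PT tables, and it may show a higher rate.

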4.8.1.3. Events Causing Death

The observation periods for patient deaths are per the observation periods defined above.

- Death on-treatment: deaths occurring during the open-label TEAE period,
- Death post-treatment: deaths occurring during the post-treatment period.

4.8.2. Laboratory Safety Variables

Clinical laboratory tests will consist of blood analyses (including hematology, clinical chemistry and other) and urinalysis. Clinical laboratory values will be converted and analyzed in both international units and US conventional units, with associated normal ranges provided by the central laboratory. Both actual test values and “change from baseline” values (defined as the post-baseline value minus the baseline value) will be used in the result summaries. Potentially clinically significant values (PCSV) ranges will be applied to the laboratory test values as applicable (see Appendix 10.4 for PCSV definitions). For those laboratory tests that do not have PCSV ranges, central laboratory normal ranges will be applied to identify out-of-range values. All laboratory test samples will be collected before study treatment administration during the protocol scheduled visits.

Unless otherwise specified below, blood samples for clinical laboratories will be collected at the protocol scheduled visits, and visits will be assigned to the Global Analysis Windows (See Appendix 10.2). The laboratory parameters (excluding those considered as efficacy parameters) will be classified as follows:

Hematology:

- Red blood cells and platelets: hemoglobin, hematocrit, erythrocytes count, red blood cells, platelets count, reticulocyte count, red blood indices
- White blood cells: white blood cells, neutrophils, lymphocytes, monocytes, basophils, eosinophils

Clinical chemistry:

- Metabolism: glucose, total protein, albumin, creatine phosphokinase
- Electrolytes: sodium, potassium, chloride, calcium, bicarbonate
- Renal function: creatinine, blood urea nitrogen (BUN), uric acid
- Liver function: ALT, aspartate aminotransferases (AST), alkaline phosphatase (ALP), total bilirubin, LDH

Other Laboratory Tests

High sensitivity C-reactive protein (hs-CRP), HbA1c.

Urinalysis

Urinalysis will include the following parameters: color, clarity, pH, specific gravity, ketones, protein, glucose, blood, bilirubin, leukocyte esterase, nitrite, WBC, RBC, hyaline and other casts, bacteria, epithelial cells, crystals, and yeast.

4.8.3. Vital Signs

Vital signs parameters will include height (cm), weight (kg), heart rate (bpm), respiration (rpm), temperature (C or F), systolic and diastolic blood pressure (mmHg) after resting at least five minutes. Both actual test values and “change from baseline” values (defined as the post-baseline value minus the baseline value) will be provided for protocol specified visits and visits will be assigned to the Global Analysis Windows (See Appendix 10.2). Potentially clinically significant

values (PCSV) ranges will be applied to the vital sign parameter values as applicable (see Appendix 10.4 for PCSV definitions).

4.8.4. 12-Lead Electrocardiography (ECG)

Electrocardiograms will be performed before blood samples are collected at visits requiring blood draws. A standard 12-lead ECG will be performed at specified time points according to Appendices 10.5 and 10.6. The ventricular rate, PR, QRS, RR, QT, QTcF, and QTcB intervals will be recorded. Electrocardiogram assessments will be described as normal or abnormal, and visits will be assigned to the Global Analysis Windows (See Appendix 10.2).

